#### 4.2.1. Inclusion Criteria

A subject will be eligible for inclusion in this study only if all of the following criteria apply:

##### 4.2.1.1. Inclusion criteria for all subjects in Parts A, B and C

1. Male or female subject aged at least 18 years at the time of signing the informed consent. The upper age limit of subjects is defined in the specific inclusion criteria for each cohort.
2. All subjects must be free from scarring or skin markings (e.g. tattoos or piercings) and open wounds on the defined areas of the body that cream will be applied onto, unless in the opinion of the investigator it will not compromise the subjects' safety and quality of data.

3. Able to refrain from exposure to extended and direct sunlight during the study period, from screening until follow up, especially the area that is under treatment during the study.
4. Able to refrain from shaving and waxing the areas on which the study cream will be applied during the duration of the study from screening to follow up.
5. Male subjects with female partners of child-bearing potential must agree to use one of the contraception methods listed in Section 4.3.1. This criterion must be followed from the time of the first dose of study medication until the follow up visit or 12 days, whichever is the latter.
6. Capable of giving written informed consent, which includes compliance with the requirements and restrictions listed in the consent form. Willing, committed and able to return for all clinic visits and complete all study-related procedures. Able to read, understand and complete study- related questionnaires.

#### **4.2.1.2. Inclusion criteria specific for healthy subjects (Part A)**

Subjects will be included in the healthy subject cohort if all the following criteria apply:

1. The subject is aged between 18 and 55 years of age inclusive, at the time of signing the informed consent.
2. Body weight  $\geq$  50 kg and BMI within the range 19 to 30 kg/m^2 (inclusive).
3. Healthy as determined by a responsible and experienced physician, based on a medical evaluation including medical history, physical examination, laboratory tests and cardiac monitoring. A subject with a clinical abnormality or laboratory parameter(s) which is/are not specifically listed in the inclusion or exclusion criteria, outside the reference range for the population being studied may be included only if the Investigator, in consultation with the GSK Medical monitor if required, agrees and documents that the finding is unlikely to introduce additional risk factors and will not interfere with the study procedures.
4. Demonstration of a positive weal and flare reaction ( $\geq$  3mm in diameter relative to negative control) to at least one allergen from a battery of allergens (**Mixed** grass pollen, Dermatophagoides pteronyssinus, birch pollen and cat dander) on skin prick testing at screening.
5. Subjects must be free from any past or present benign or malignant skin conditions and disease, unless in the opinion of the investigator it will not compromise the subjects' safety and quality of data.
6. Non –smokers or if the subject is a tobacco smoker: smokes less than 5 cigarettes per day and commits to not smoke tobacco for the duration of the in-house stay, and commits to stable and moderate use (as determined by the Investigator) of tobacco or nicotine-containing products, including nicotine patches/gum, during the course of the study, as long as the patches do not interfere with the study procedures.
7. A female subject is eligible to participate if she is of:

- Non-childbearing potential defined as pre-menopausal females with a documented tubal ligation or hysterectomy for this definition, “documented” refers to the outcome of the investigator's/designee's review of the subject's medical history for study eligibility, as obtained via a verbal interview with the subject or from the subject's medical records; or postmenopausal defined as 12 months of spontaneous amenorrhea in questionable cases a blood sample with simultaneous follicle stimulating hormone (FSH) > 40 MIU/ml and estradiol < 40 pg/ml (<147 pmol/L) is confirmatory.
- Females on hormone replacement therapy (HRT) and whose menopausal status is in doubt will be required to use one of the contraception methods described if they wish to continue their HRT during the study. Otherwise, they must discontinue HRT to allow confirmation of post-menopausal status prior to study enrolment. For most forms of HRT, at least 2-4 weeks will elapse between the cessation of therapy and the blood draw; this interval depends on the type and dosage of HRT. Following confirmation of their post-menopausal status, they can resume use of HRT during the study without use of a contraceptive method.

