#### 3.2.1.1. Part A: Healthy Subject Cohort

Healthy male and female subjects (female subjects who are of non-child bearing potential will be included in Part A of the study) will be assessed for safety, tolerability, pharmacokinetics (PK) and pharmacodynamics (PD) after once or twice daily dosing of GSK2646264. Safety assessments over the day 1 dosing period will enable a repeat dose period with increasing body surface and safety assessment from days 1 through to day 3 in group 1. Also, based on the current understanding of SYK kinase inhibition, it is anticipated that target engagement will be determined by the pharmacodynamic endpoint of allergen challenge.

Safety and tolerability in these subjects will also enable covering an increase in strength and increasing body surface area from days 1 through to day 4 of the dosing period in group 2. In addition, PK will drive the decision of whether group 2 will be dosed once or twice daily. Safety, tolerability and systemic exposure data including any effect on IgM stimulated CD69 generated in Part A will be used to provide margins for the strength of GSK2646264 applied and also the body surface area (BSA) covered in cold urticaria subjects in Part B and in chronic spontaneous urticaria subjects in Part C.

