Pregnancy and lactation	
There is no data available on the effect of GSK 2646264 in pregnancy and lactation in humans.
 
Fetal malformations were seen after IV dosing to pregnant rabbits with a NOAEL that is expected to exceed the highest expected human exposure by >4 fold. No similar changes were seen in the rat after substantially higher exposure
	
Female subjects of non child bearing potential will be included in Part A of the study.
 
Female subjects that are of child-bearing potential will be required to follow the contraceptive requirements that are outlined in the protocol Section 4.2.1 inclusion criteria for Part B and C.
 
A decision to allow females of child-bearing potential in Parts B and C will be made based on the safety margin from the dosing in Part A of the study.
	
Female subjects that are of child-bearing potential will undergo regular pregnancy testing and treatment stopped immediately if a subject is found to be pregnant during the study.
 
In part B, these subjects must be on oral contraceptives 28 days before screening begins. They will undergo serum pregnancy testing at day -28, day -7 to -4, a serum or urine pregnancy test the day of the start of the study prior to dosing, then testing on an approximately weekly basis and a serum pregnancy test at the follow up visit.
 
In Part C, a serum pregnancy test will be

Potential risk	Summary of data	Impact- eligibility criteria	Strategy-monitoring/stopping criteria
		Nursing females will be excluded from participating in the study.	performed on the day of screening. If this is between Days -13 and -7, a further pregnancy test will not be required until Day 1. However, if the day of screening is between Day -28 and -14, an additional serum pregnancy test will be required between Days -7 and -4. A urine pregnancy test will be required prior to dosing on Day 1

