13. A positive drug screen at screening or Day -1 (parts A & B only). For Part B patients, a positive drug screen due to concomitant medication may be acceptable for inclusion in the study based on the Investigator's opinion. The Investigator's opinion must be based on interview of the subject, documented in the medical history and the Investigator is asked to document that the positive test can be explained by a relevant and permitted medication (see Section 5.15.1.) and that the medication will not interfere with the study procedures or compromise subject safety. A drug screen will not be performed in Part C.
14. Lactating females.
15. Where participation in the study would result in donation of blood or blood products in excess of 500 mL within a 56 day period.
16. The subject has participated in a clinical trial and has received an investigational product within the following time period prior to the first dosing day in the current study: 30 days, 5 half-lives or twice the duration of the biological effect of the investigational product (whichever is longer).
17. Exposure to more than four new chemical entities within 12 months prior to the first dosing day
18. Use of topical steroids or calcinurin inhibitors is prohibited during the study from screening to follow up (See Section 5.12).
19. Exclusion related to prior drug treatments:
  - a) Intake of oral corticosteroids within 7 days >10mg/day prior to first screening visit.
  - b) Use of depot corticosteroids within 7 days prior to first screening visit.
  - c) Subjects who are taking anticoagulants (e.g. warfarin) must not be on warfarin within 21 days prior to screening. (See Section 5.15).
  - d) Subjects who are having psoralen combined with ultraviolet A (PUVA) treatment must not be using PUVA treatment within 21 days prior to screening.

20. Subjects who work for the Sponsor, Contract Research Organisation (CRO), or one of the study centres.

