### **4.3. Lifestyle and/or Dietary Restrictions**

#### **4.3.1. Contraception Requirements**

##### **4.3.1.1. Female Subjects**

In Part A: Female subjects of non-childbearing potential will be recruited onto the study.

In Parts B and C: Female subjects of child bearing potential may be recruited onto the study, and must not become pregnant and so must be sexually inactive by abstinence or use contraceptive methods with a failure rate of < 1%. Female subjects of childbearing potential with same sex partners are not required to be abstinent or to use contraception. Subjects in parts B and C will need to be on established contraceptive as listed in Section 4.2.1 inclusion criteria at the time of screening (day -28) and will have regular serum/urine pregnancy testing throughout the duration of the study as listed in the Time and Events Table Section 6.1. Contraceptive use shall be continuous through the pre-study, study and follow-up periods of the study.

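### Part A's HRT criterion admits a woman whose fertility is uncertain, although other sections limit Part A to women of non-childbearing potential and its schedules contain no pregnancy test

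*Protocol*

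**What the plan says.** Three places in the protocol describe the women in Part A in the same way. Section 3.2.1.1 says that "female subjects who are of non-child bearing potential will be included in Part A of the study". Section 4.3.1.1 says "In Part A: Female subjects of non-childbearing potential will be recruited onto the study". Table 6 (pregnancy and lactation row) agrees, and leaves the admission of women of child-bearing potential to Parts B and C, to be decided on the safety margin seen in Part A.

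The Part A inclusion criterion for women (section 4.2.1.2, criterion 7) has two bullets. The first defines non-childbearing potential. The second concerns HRT users with doubtful menopausal status, who "will be required to use one of the contraception methods described if they wish to continue their HRT during the study". The bullet then gives the alternative for those who do not take that route: "Otherwise, they must discontinue HRT to allow confirmation of post-menopausal status prior to study enrolment".

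For contraception and testing, section 4.3.1.1 states that "Subjects in parts B and C will need to be on established contraceptive", with regular pregnancy tests as scheduled. It has no equivalent duty for Part A.

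On eligibility, exclusion item 14 in section 4.2.2, which applies to all cohorts, reads in full "Lactating females". Table 6 matches it: "Nursing females will be excluded from participating in the study". No inclusion or exclusion criterion names pregnancy or a positive pregnancy test.

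**The concern.** The second bullet of criterion 7 asks for contraception, which makes sense only if the woman might be fertile. The rest of the protocol treats Part A as a population in which no woman is fertile, and its safeguards are built on that assumption. A woman who enters through this bullet therefore meets none of the safeguards provided for women of child-bearing potential in Parts B and C.

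This is the first-in-human part. Table 6 reports fetal malformations in rabbits. Section 4.2 says that adherence to the criteria as written is essential and that deviations are not allowed, so the exact wording decides who may be dosed.

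**Working it through.** No sample size or other statistical figure is involved. The check sets the passages side by side.

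1. **Is confirmation of menopausal status required on both HRT routes?** No. The sentence requiring HRT to be stopped so that status can be confirmed opens with the word for an alternative. It applies to women who do not continue HRT on contraception. A woman on the first route enters with her status still in doubt.

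2. **Is she within the Part A age range?** Yes. Part A takes subjects aged 18 to 55.

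3. **Is she tested for pregnancy in Part A?** The dose group 1 schedule (6.1.1) has no pregnancy-test row, nor does the dose group 2 schedule (6.1.2). The SAP copies (Appendix 2, 11.2.1.1 and 11.2.1.2) have none either. The reproductive-status tests in section 6.3.4 are FSH and estradiol, as needed, for women of non-childbearing potential.

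4. **How does that compare with Part B?** Note 4 of section 6.1.3 gives serum tests at Day -28 and between Days -7 and -4, a serum or urine test on Day 1 before dosing, a serum test between Days 10 and 12, and a serum test at follow-up: 3 before the first dose + 2 after = 5. Part A has 0.

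5. **Is her contraception specified as it is in Parts B and C?** In those parts (4.2.1.3 criterion 9, 4.2.1.4 criterion 8) it must be in use for at least 28 days before screening and continue to follow-up or 12 days after the last dose, whichever is longer. The Part A bullet states neither a lead-in nor a period after the last dose.

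6. **What happens to a pregnancy found before dosing in Parts B and C?** Section 6.1.3 requires a pre-dose test on Day 1, as above. Section 6.1.4 requires a serum test at screening (with a further one if screening falls between Days -28 and -14) and a urine test before dosing on Days 1 and 7. A pregnancy would therefore be looked for before the first dose. Table 6 then stops treatment if a subject is found pregnant during the study.

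7. **What do the remaining rules cover?** Section 7.2.1 collects pregnancies after dosing has started. Section 7.2.2 withdraws a woman who becomes pregnant while taking part. Neither is worded for a positive result at screening or before the first dose. The criteria do not mention one, so the Table 6 sentence is the only pregnancy-specific text that reaches it.

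Steps 1 to 5 establish the Part A conflict. Steps 6 and 7 show that Parts B and C have a working safeguard, but that the eligibility list does not state it.

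**The case against.** A reader might infer something stronger: because no criterion in any part excludes a positive test, a woman known to be pregnant could be dosed in Part B or C. The documents do not support that. Tests are placed before the first dose, and Table 6 acts on a detected pregnancy. In addition, 4.2.1.3 criterion 5 and 4.2.1.4 criterion 7 admit an unlisted out-of-range laboratory finding only if the investigator documents that it is unlikely to add risk. A positive test plausibly falls under those criteria, and that statement would be hard to make beside the rabbit findings. This part of the objection stands. A similar criterion exists in Part A (4.2.1.2 criterion 3), but it cannot act on a test that is never scheduled.

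The second objection is that the Part A problem is narrow and mostly past. It concerns only women of 55 or under, on HRT, with doubtful status and on contraception that section 4.3.1.1 lists as failing in under 1%. Sections 3.2.2.2 and 3.2.3 already report Part A data. This also stands and limits the point to future use. Section 5.5.3.2 still allows cohorts to be expanded or added under the same procedures, but nothing says that any are planned.

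Third, exposure in Part A does not by itself show harm. Appendix 6 implies a fetal AUC NOAEL of about 3.6 x 61.4 = 221 ng.h/mL. Against the preliminary Part A geometric mean of 103.8 ng.h/mL (section 3.2.2.2) the margin is 221 / 103.8 = 2.1. Section 3.2.2.3 accepts a 1.8-fold margin for women of child-bearing potential. The margin therefore should not be cited as the size of the problem. The point rests on the contradiction and the missing test.

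Finally, the second bullet might be read as a note on proving non-childbearing status. That reading does not account for the first HRT route, which ends in contraception and not in proof.

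**Conclusion.** The Part A contradiction holds. Criterion 7 admits a woman whose menopausal status is unconfirmed, three other places limit Part A to women of non-childbearing potential, and neither Part A schedule tests for pregnancy. The protocol followed exactly permits a possibly fertile, untested woman to be dosed.

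Its practical size is small. Part A was planned for 18 subjects, 9 per dose group. The documents do not say how many, if any, entered through the HRT route. Looking forward, only cohorts added under section 5.5.3.2 could be affected, assuming that any such cohort uses the Part A criteria and schedules.

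In Parts B and C the finding is a drafting gap and not a route to dosing a pregnant woman. The criteria name lactation only and do not state what a positive screening or pre-dose test means for eligibility. This rests on the tests being done as scheduled and on a test before dosing counting as part of the study for the Table 6 rule. It is worth correcting because it bears on safety and is cheap, but it does not call the trial's conduct or results into question.

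**What to change.** Two sets of passages need to be reconciled.

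- **Part A:** section 4.2.1.2 criterion 7 with sections 3.2.1.1 and 4.3.1.1, Table 6 and the schedules in 6.1.1 and 6.1.2, so that the female population and its assessments agree.
- **Parts B and C:** the eligibility criteria, including exclusion item 14 in section 4.2.2, with Table 6, section 7.2.2 and the schedules in 6.1.3 and 6.1.4, so that the protocol says in one consistent way what a positive screening or pre-dose test means.

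Which clinical rule to adopt in either case is for the sponsor to decide. The cost is a few lines of protocol wording, plus whatever assessments follow from that decision for the few women concerned. The statistical analysis is unaffected.

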#### **4.2.1.3. Additional Inclusion criteria specific for subjects with cold urticaria (Part B)**

Subject will be included in the cold urticaria subject cohort if all the following criteria apply:

1. Diagnosed with cold urticaria for more than six weeks as confirmed by medical history and with a positive cold stimulation test assessed by TEMPTest 4.0 prior to first dose.
2. The subject is aged between 18 and 70 years of age inclusive, at the time of signing the informed consent.
3. Body weight  $\geq 50$  kg and BMI within the range 19 to 35 kg/m^2 (inclusive).
4. Other than a diagnosis of cold urticaria, the subject should have no other co-morbidities which would introduce additional risk factors and will not interfere with the study procedures, as determined by a responsible and experienced physician, based on a medical evaluation including medical history, physical examination, laboratory tests and cardiac monitoring.
5. A subject with a clinical abnormality or laboratory parameter(s) which is/are not specifically listed in the inclusion or exclusion criteria, outside the reference range for the population being studied may be included only if the Investigator, in consultation with the GSK Medical monitor if required, agrees and documents that the finding is unlikely to introduce additional risk factors and will not interfere with the study procedure.
6. In addition, the following criterion will apply to a minimum of 4 patients in Part B:

Demonstration of a positive weal and flare reaction ( $\geq 3$  mm relative to negative control) to at least one allergen from a battery of allergens (**mixed** grass pollen, *Dermatophagoides pteronyssinus*, birch pollen and cat dander) on skin prick testing at screening,

7. Subjects must be free from any past or present benign or malignant skin conditions and disease, other than the specified condition required for eligibility of subjects as defined in the specific inclusion criteria for CU cohort unless in the opinion of the investigator it will not compromise the subjects safety and quality of data.
8. Non-smokers or if the subject is a tobacco smoker: smokes less than 5 cigarettes per day and commits to not smoke tobacco for the duration of the in-house stay, and commits to stable and moderate use (as determined by the Investigator) of tobacco or nicotine-containing products, including nicotine patches/gum, during the course of the study, as long as the patches do not interfere with the study procedures.
9. Female subjects of child bearing potential must have been using one of the contraception methods listed in Section 4.3.1 at least 28 days before their screening visit and agree to continue with these methods until the follow up visit or 12 days after the last dose of study treatment, whichever is the longer.

If a patient who has been screened and is eligible for the study becomes unavailable to do the study at the initially planned dates due to exceptional circumstances, the subject may be re-screened for the study; in total a patient may be screened 2 times. This will only be at the discretion of the Investigator.

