**Table 3 Treatment applied to specified areas per day on Part A; healthy subjects, n=9, dose group 2**

	Day 1-2	Day 3-4	Day 5 to 7
Area	AM a	AM a	
Left Arm	0.36g of 1.0% b GSK2646264 or placebo cream applied to 36cm  (~0.2% BSA)		NO DOSING
Right Arm	0.36g of 1.0% b GSK2646264 or placebo cream applied to 36cm  (~0.2% BSA)		NO DOSING
Left Torso	9g of 1.0% b GSK2646264 or placebo cream applied to 900cm  (~5% BSA)	9g of 1.0% b GSK2646264 or placebo cream applied to 900cm  (~5% BSA)	NO DOSING
Right Torso	9g of 1.0% b GSK2646264 or placebo applied to 900cm  (~5% BSA)	9g of 1.0% b GSK2646264 or placebo cream applied to 900cm  (~5% BSA)	NO DOSING

a. AM dosing only

b. 0.5% strength may be used if data for Part A and/or group 2 supports

**3.1.4. Part B: A double blind (sponsor unblinded) placebo-controlled, randomised to active or placebo treatment, three day repeat dose study, in cold urticaria subjects**

Subjects will be randomised in a 3:1 ratio to receive either active treatment or placebo applied to defined areas once a day for 3 days. The first 4 subjects of Part B will be randomised so that one of the four subjects will receive placebo and the three other subjects will receive GSK2646264. An interim review of the preliminary data from the first 4 subjects, after they have completed the study, will be conducted before dosing the rest of the patients in Part B (n=12 total). PK, safety and tolerability preliminary data up to and including the follow-up visit, will be reviewed by the SMC (See Section 5.5). See Figure 3 for a visual representation.

If preliminary data indicates it is appropriate to review additional PD data, this may then be conducted, either in parallel to or before the remainder of Part B subjects are enrolled.

Criteria to choose dose strength and dose regime in Part B are detailed in Section 5.5. Further dose adjustments may be made as a result of reviewing preliminary data from the first n=4 subjects in Part B.

This cohort will remain in-house for the whole dosing period (until completion of the final dose on the morning of day 3) and completion of subsequent study assessments on day 4.

The timing of the assessments to be completed at each visit are provided in the Time and Event table (Section 6.1.3).

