### 3.1.4.1. Changes after review of preliminary data of n=4 from Part B by the Safety Monitoring Committee

[figure not shown]
Following the review by the Safety Monitoring Committee (see Section 5.5), changes were made to Part B for the remaining n=8 subjects, as shown in [Table 5](#).

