**Table 5 Part B: Cold urticaria treatment (remaining n=8 subjects)**

	Days 1-3
Area	Morning dosing
Both Arms	6.3g of 1% strength GSK2646264 or placebo to be applied to a total area of 630cm  (3.5% BSA), spread over the 2 arms, and the volar aspect must be included. The investigator should use their discretion as to how much cream is applied to each arm, but it must be equivalent to 3.5% BSA in total.

Following inclusion subjects will be randomised to either active or placebo. The investigator will use his judgement and discretion to decide on which area to apply the study treatment within requirements given in [Table 4](#).

Subjects will receive either 1% strength GSK2646264 cream or placebo cream. The skin prick test will be performed on the volar aspect of the arm only in subjects who have a positive allergen challenge test at screening, as per inclusion criteria.

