## 4. STUDY POPULATION

### 4.1. Number of Subjects

The aim is to achieve approximately 18 randomised evaluable subjects in Part A (9 subjects in dosing group 1 and 9 subjects in dosing group 2), approximately 12 randomised evaluable subjects who complete the study in Part B and approximately 16 subjects in Part C. In Parts A and B, it is anticipated that a proportion of subjects will not demonstrate weal and flare at the screening skin prick test (See Section 4.2.1.2 and Section 4.2.1.3). However these proportions are not known, so enough subjects will be enrolled to achieve the target study population.

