## 5.4. Treatment Assignment

Subjects will be assigned to treatment in accordance with the randomization schedule generated by Parexel, prior to the start of the study. Randomisation will occur within each cohort of study. Subjects will be randomised to 1:1 to receive bilateral treatment of GSK2646264 or placebo in Part A. For Parts B & C, subjects will be randomised 3:1 active:placebo respectively, to receive either GSK2646264 or placebo.

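### Part B's minimum of 4 skin-prick-positive patients was kept when the design became parallel 3:1 without stratification; if only that minimum is met, there is a 25.5% chance that no placebo patient has on-treatment allergen-challenge data

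*Protocol*

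**What the plan says.** - **Who must be positive.** Protocol 4.2.1.3, criterion 6: "In addition, the following criterion will apply to a minimum of 4 patients in Part B". The criterion is a positive weal and flare reaction to at least one allergen at screening.
- **Who is tested on treatment.** The text below Table 5 in protocol 3.1.4.1 says that the skin prick test is done "only in subjects who have a positive allergen challenge test at screening".
- **Size.** Protocol 4.1 plans "approximately 12 randomised evaluable subjects who complete the study in Part B".
- **Allocation.** Protocol 5.4: "For Parts B & C, subjects will be randomised 3:1 active:placebo respectively, to receive either GSK2646264 or placebo". The same section says "Randomisation will occur within each cohort of study". Neither the protocol nor the SAP mentions a stratum or allocation rule based on skin-prick status.
- **Staging.** Protocol 3.1.4 fixes the first four patients so that "one of the four subjects will receive placebo and the three other subjects will receive GSK2646264". After their data were reviewed, "changes were made to Part B for the remaining n=8 subjects" (3.1.4.1).
- **Endpoint.** Protocol 2.3.2 lists percent inhibition of weal and flare measures on Day 3 as an exploratory Part B endpoint. Section 3.2.1.2 names allergen challenge and the critical temperature threshold as the two measures expected to show target engagement.
- **Timing.** In protocol 6.1.3, screening ends at Day -7 and randomisation is on Day -1. The skin prick test is done before the first dose on Day 1, 6 hours after the Day 3 dose, and 24 hours after the last dose.
- **History.** The amendment log (protocol Appendix 8) shows the same minimum of 4 at Amendment 2, when Part B was bilateral. Amendment 3 made Part B parallel, and the minimum is unchanged in the current text.

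**The concern.** Under the bilateral design, 4 positive patients meant 4 within-patient comparisons of active with placebo. Under the parallel design, the same 4 patients are divided between two arms at 3:1, so the expected number on placebo is one. Nothing in the allocation prevents it from being none.

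At stake is the placebo reference for the Part B allergen challenge. Protocol 9.1.1 describes the study as designed to estimate the effect relative to placebo, and the SAP (11.3.2.2) defines percent inhibition against a control value. If all positive patients are on active treatment, no placebo patient supplies that value.

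**Working it through.** The documents give no probability or precision figure for Part B (Table 10 covers Part A only), so there is no planned figure to reproduce.

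**Inputs**
- 12 patients (protocol 4.1) at 3:1 (5.4): 12 × 3/4 = 9 active and 12 × 1/4 = 3 placebo.
- First 4 patients: 3 active, 1 placebo (3.1.4). Remaining 8 (3.1.4.1): 6 active, 2 placebo if 3:1 holds exactly.
- Number of positives, k: at least 4 (4.2.1.3). Section 4.1 says the proportion is not known, so any k above 4 is an assumption.
- Assumption: skin-prick status is unrelated to order of entry.

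**Step 1: chance that no positive patient is on placebo, current plan**

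P(none) = C(9,k) / C(12,k). For k = 4 this is 126/495 = 25.5%.

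**Step 2: chance of at most one, k = 4**

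P(exactly one) = 3 × C(9,3) / C(12,4) = 252/495 = 50.9%. P(at most one) = (126 + 252)/495 = 378/495 = 76.4%. The expected number is 4 × 3/12 = 1.

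**Step 3: does the randomisation mechanism matter?**

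Fixing the first four at 3:1 and averaging over where the 4 positives fall also gives 25.5%. Independent 3:1 allocation of each patient would give 0.75^4 = 31.6%. If all 4 positives were the first four patients, the chance would be 0.

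**Step 4: effect of stratifying the last 8**

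Let a positives be among the first four patients and b = k − a among the last 8, with weight C(4,a) × C(8,b) / C(12,k). With blocks of 4 holding one placebo in the positive stratum, P(none) = (4 − a)/4 × (4 − b)/4 for b below 4, and 0 for b of 4 or more.
- k = 4: a = 1 gives 224/495 × 3/4 × 1/4; a = 2 gives 168/495 × 2/4 × 2/4; a = 3 gives 32/495 × 1/4 × 3/4; a = 0 and a = 4 give 0. Sum: (42 + 42 + 6)/495 = 90/495 = 18.2%.
- k = 5: a = 2 gives 336/792 × 2/4 × 1/4; a = 3 gives 112/792 × 1/4 × 2/4; the rest give 0. Sum: (42 + 14)/792 = 56/792 = 7.1%.
- k = 6: only a = 3 contributes: 224/924 × 1/4 × 1/4 = 14/924 = 1.5%.
- k = 8: at least 4 positives fall among the last 8, so 0.

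| Positives among 12 | P(none on placebo), current plan | P(none on placebo), last 8 stratified |
|---|---|---|
| 4 | 126/495 = 25.5% | 90/495 = 18.2% |
| 5 | 126/792 = 15.9% | 56/792 = 7.1% |
| 6 | 84/924 = 9.1% | 14/924 = 1.5% |
| 8 | 9/495 = 1.8% | 0 |

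**The case against.** **The figure is conditional.** A reader might infer that Part B runs a one-in-four risk as it stands. The documents do not support that. Criterion 6 sets a floor, not a target, and the risk falls quickly above it. The first four patients, one on placebo, had already been reviewed. If that placebo patient was positive, the risk is already zero; the documents do not report skin-prick status. This objection stands, and it is why the figure must carry its condition.

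**The endpoint would not be lost entirely.** A reader might infer that it could not be estimated at all. That goes too far. Protocol 2.3.2 states a placebo comparison for the cold test but not for the allergen challenge, and the Day 1 pre-dose test gives each positive patient an own starting value. The SAP assigns this test no baseline (11.3.2.1), but the SAP is written for Amendment 2 and its bilateral design, so it does not settle the current calculation. A change from pre-dose in active patients could be described. It would be uncontrolled, so the loss of the placebo reference stands.

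**The stakes are limited.** The endpoint is exploratory and descriptive, and the sample size rests on feasibility. Part A requires every subject to be positive and uses each as their own control, and the Part B cold test does not depend on skin-prick status. This lowers the priority but does not remove the defect.

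**One placebo patient is a weak reference.** That is true. The change guards against having none; it does not make the comparison precise.

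**Section 4.1 is not a contradiction.** A reader might take "so enough subjects will be enrolled to achieve the target study population" to mean that negative Part B patients must be replaced. The sentence does not say so. The paragraph refers to 4.2.1.3, so the target can include the minimum-of-4 rule.

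**Conclusion.** The point holds in conditional form. The current protocol guarantees 4 skin-prick-positive Part B patients and does nothing to spread them across arms. At that minimum, the chance of no positive placebo patient is 25.5%, and the chance of at most one is 76.4%. The chance of none is 15.9% with 5 positives, 9.1% with 6 and 1.8% with 8. These figures assume exactly 12 patients, an exact 9:3 split, and skin-prick status unrelated to order of entry. The consequence is loss of the placebo reference for one exploratory endpoint, leaving an uncontrolled pre-to-post description. It warrants a low-cost change to the allocation, not a larger trial.

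**What to change.** In protocol 5.4, make screening skin-prick status a stratum for the Part B patients still to be randomised, with 3:1 blocks of 4 in the positive stratum. Status is known before Day -1, so no procedure is added. The unblinded group that prepares the randomisation list should take account of positives already allocated, so that at least one positive patient is on placebo where possible. This condition should not go into criterion 6: the site staff who apply eligibility are blinded and could not check it.

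**Cost.** A revised list for the remaining patients and a short amendment to 5.4. No extra patients are needed.

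**Limits**
- The guarantee is only partial if some positives are already on active. For example, with 2 positives on active in the first four and 2 more to come, fresh blocks of 4 leave a 2/4 = 50% chance of none, against C(6,2)/C(8,2) = 15/28 = 54% without strata. This is why the list should reflect earlier allocations.
- Incomplete blocks can move the overall ratio. If the last 8 are 5 positive and 3 negative, with blocks of 4 in each stratum, the positives contain 1 or 2 placebo patients and the negatives 0 or 1. The total is then 1 to 3 instead of 2.
- The reductions in the table assume that all 8 remaining patients are still to be randomised. The benefit shrinks as that number falls.
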